7.3 Exploratory Analyses

All primary and secondary efficacy endpoints will be reanalysed in the Per-protocol population.

If available in a suitable timeframe before reporting, immunologic response data will be listed in the CSR. If applicable, summaries and exploratory analyses will be specified in a separate analysis plan and presented in a separate report.

The following endpoints will be analysed:

- immunologic response of PBMCs,
- total PBMC counts by flow cytometry,
- evaluation of tumour tissue obtained from pre-treatment resection for antigen expression by immunohistochemical analysis,
- evaluation of tumour tissue obtained from repeat biopsy, if clinically indicated, for presence of infiltrating T-lymphocytes,
- T cell receptor sequencing of peripheral blood T cells before and during the course of treatment
- Tissue immune cell infiltration, and inflammatory cytokine levels in urine

8 Safety Analyses

Safety comparisons will be performed on all patients who received at least one dose of experimental treatment in both phases of the study. The safety variables to be analyzed include vital sign measurements, AEs, ECGs, routine hematology, coagulation factors, serum chemistry, urinalysis, and deaths. Unless otherwise noted, safety variables will be tabulated by descriptive statistics (n, mean, median, SD, minimum, and maximum; or n and percent) using the Safety Population. When calculating the incidence of adverse events, or any sub-classification thereof by treatment, time period, severity, etc., each subject will only be counted once and any repetitions will be ignored; the denominator will be the total population (or treatment group, as applicable) size. A descriptive summary of all Treatment emergent adverse events (TEAEs) by system organ class and preferred term will be provided.

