-  PE at screening and Week 56 (End of Treatment) will have a full examination of body systems and vital signs. Other PE evaluations will be limited to symptoms, weight and vital signs.
-  70mL of heparinized blood, 10mL of non-heparinized blood, and 24mL urine will be collected at the indicated visits.
-  ANA, TSH, ESR, C-reactive protein are required. Other tests (e.g. RF, T3, T4, thyroid antibodies) will be performed only as clinically indicated.
-  All patients will have a cystoscopy/cytology performed at Week 13. If clinically indicated, a repeat biopsy will be performed. Patients with evidence of disease at an assessment may continue on treatment if judged by the investigator to be in the patient's best interest (e.g. would normally receive another course of BCG therapy as SOC). Upon discontinuation of study treatment, additional treatment will be at the discretion of the treating physician, and patients will continue in long-term follow-up on the study.
-  For Arms 1-4: Patients will receive study product as the number of intradermal injections required to reach the number of cells per dose with no more than 0.1 mL per injection (approximately 4-6 injections). Patients should remain on site for 30 minutes following each vaccination for observation of adverse events.
-  For Arms 1-3 only.
-  Includes eye exam for dry eyes, lymph node and joint assessment and skin exam for vitiligo and rashes.
-  AEs should be recorded from first dose through four weeks following the last dose of study medication regardless of the causal relationship to the study medication. AEs considered related to study medication should be recorded at any time regardless of when they occurred.
-  Samples to be collected prior to dosing
-  Cystoscopy/Cytology for disease recurrence per SOC (approximately every 3 months for 2 years then every 6 months for up to a year). Patients who are determined to have evidence of disease will have SOC treatment per the discretion of the investigator and will continue in long-term follow-up on the study.
-  Weekly study evaluations should be completed within  $\pm 3$  days of the target visit date.

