## **11.8 Adverse Events (AE) and Serious Adverse Events (SAE)**

The investigator is responsible for the detection and documentation of events meeting the criteria and definition of an AE or SAE, as provided in this protocol. During the study when there is a safety evaluation, the investigator or site staff will be responsible for detecting, documenting, and reporting AEs and SAEs, as detailed in both this section of the protocol and in the AE/SAE section of the study procedures manual. AEs should only be recorded for up to four weeks following the last dose of study medication, unless the AE is considered related to the study medication, which requires that the AE be reported regardless of the amount of time that has passed since receiving the last dose of study medication.

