#### **12.4.1 Adverse Events**

Treatment emergent adverse events (TEAEs) will be defined as events that occur on or after the first dose of study medication. The Medical Dictionary for Regulatory Activities (MedDRA) coding dictionary will be used for the coding of AEs. TEAEs, serious or CTC Grade 3 or 4 TEAEs, and TEAEs related to therapy will be summarized overall and by system organ class and preferred term by treatment group. These will summarize the number of events and the number and percent of patients with a given event. A Fisher's exact test will be provided to evaluate if the number of patients with an event within a specific system organ class is homogeneous across the treatment groups. In addition, the number and percent of patients with TEAEs will be provided by maximum severity. A summary of all TEAEs by system organ class and preferred term occurring in at least 5% of subjects in either treatment group will be provided by quarter.

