8.2 Adverse Events

TEAEs will be defined as events that occur on or after the first dose of study medication. The Medical Dictionary for Regulatory Activities (MedDRA) coding dictionary will be used for the coding of AEs (version 18.0 or higher). The severity of TEAEs will be graded on a scale of 1 to 5 according to the adult NCI Common Terminology Criteria for Adverse Events (CTCAE version 4.0) where higher grades indicate events of higher severity. Adverse events will be summarized by grade according to the worst grade experienced. TEAEs, serious or CTCAE grades -5 TEAEs, and TEAEs related to therapy will be summarized overall and by system organ class and preferred term by treatment group. A listing of AEs leading to treatment discontinuation including the patient number, site, treatment group, start date and study day of AE, severity, relationship to study regimen, action taken, and outcome of AE will be provided. Additional summary table summarizing preferred term may be provided if warranted.

For summary purposes, AEs will be defined as all reported events with a start date on or after Study Day 1. All AEs are collected through 30 days post last dose (treatment-emergent AEs). All AEs will have their relationship to study drug (BCG or HS-410) assessed by the investigator as related or not related. Adverse events will be categorized and summarized according to their highest relationship to study drug.

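### AE percentages by time period keep patients in the denominator after AE recording has ended, so later quarters understate incidence in the arms where more patients stop dosing

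*SAP*

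**What the plan says.** SAP section 8 sets one counting rule for AE incidence "or any sub-classification thereof by treatment, time period, severity, etc., each subject will only be counted once", and then fixes the divisor: "the denominator will be the total population (or treatment group, as applicable) size". Time period is named, so the rule governs by-period tables as well as the overall one.

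Protocol 12.4.1 plans such a table. The common treatment-emergent AEs, those "occurring in at least 5% of subjects in either treatment group will be provided by quarter", are broken down over time.

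AE recording is limited. Protocol 11.8 says "AEs should only be recorded for up to four weeks following the last dose of study medication", with one exception, given also in the notes to the Phase 2 Schedule of Events: "AEs considered related to study medication should be recorded at any time regardless of when they occurred". SAP 8.2 puts the end of AE collection at 30 days after the last dose rather than four weeks.

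Protocol 7.2.1 lists progressive disease among the reasons for which dosing will be discontinued. Recurrent disease is among the reasons for which it may be, at the investigator's judgement.

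SAP 8.1 summarises doses and exposure by arm. Neither document plans an at-risk denominator or an exposure-adjusted AE rate.

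**The concern.** How long a patient is observed for all-cause AEs depends on how long the patient is dosed, and that depends partly on efficacy. A patient who stops at the Week 13 cystoscopy leaves all-cause AE recording early in the second quarter but stays in the divisor for the third and fourth. The table then treats an unobserved patient as one who was observed and had no event.

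If arms fail at different rates, the later columns differ even when the true AE rates are the same. Safety of the combination is a secondary objective, and Protocol 12.4.7 defines it as a comparison of AE/SAE proportions between vaccine plus BCG and placebo plus BCG. Under the plan's own efficacy assumption, placebo loses more patients from observation. The artefact would then look like late-onset vaccine toxicity.

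**Working it through.** **Inputs.** The documents give no expected AE percentage, so there is no planned AE figure to reproduce. The failure rates come from the sample-size assumption in Protocol 12.6.2: one-year disease-free survival (DFS) of 60% on control and 90% on each vaccine arm. That assumption is coherent with the stated 80% power: the exact one-sided Fisher test at 0.10 with 23 evaluable per arm gives 80.8%. From Protocol 6.2.1 and 6.2.3, cystoscopies fall on days 85, 169, 253 and 337. The last dosing days before them are 78, 106, 190 and 190. The last scheduled dose is on day 358 and the End of Treatment visit on day 386.

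**Step 1: failures per cystoscopy.** With equal hazard at each of four looks, h = 1 − DFS^(1/4), which is 0.1199 for placebo and 0.0260 for vaccine. The probabilities of failing at looks 1 to 4 are:
- placebo: 12.0%, 10.6%, 9.3%, 8.2% (sum 40%)
- vaccine: 2.6%, 2.5%, 2.5%, 2.4% (sum 10%)

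**Step 2: end of AE observation for a patient who stops.** Three readings are tried; everyone else is observed to day 386.
- A, last dose plus 28 days: 106, 134, 218, 218
- B, the stopping visit, but not before A: 106, 169, 253, 337
- C, stopping visit plus 28 days: 113, 197, 281, 365

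**Step 3: share of days 274 to 386 (113 days) observed, if all failing patients stop.**
- A: 60.0% and 90.0%.
- B: look-4 stoppers add 64/113 = 0.566 of the period. Placebo 0.60 + 0.0817 × 0.566 = 0.646; vaccine 0.90 + 0.0240 × 0.566 = 0.914.
- C: look-4 stoppers add 92/113 = 0.814 and look-3 stoppers 8/113 = 0.071. Placebo 0.60 + 0.0817 × 0.814 + 0.0929 × 0.071 = 0.673; vaccine 0.90 + 0.0240 × 0.814 + 0.0247 × 0.071 = 0.921.

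If only a fraction s of failing patients stops, the share is 1 − s(1 − share above). With a full-arm divisor and the same constant, low AE rate in both arms, the reported percentage is proportional to this share.

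| Rule | All stop: placebo / vaccine / ratio | Half stop: placebo / vaccine / ratio |
|---|---|---|
| A | 60.0% / 90.0% / 1.50 | 80.0% / 95.0% / 1.19 |
| B | 64.6% / 91.4% / 1.41 | 82.3% / 95.7% / 1.16 |
| C | 67.3% / 92.1% / 1.37 | 83.7% / 96.1% / 1.15 |

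If none stop, the ratio is 1.00.

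**Step 4: a second model.** Spread failures evenly over the four looks, set the true risk at 20% per quarter in both arms, and end the fourth quarter at day 365. The range in each figure runs from rule A to rule C.
- All stop: 12.0–14.2% on placebo, 18.0–18.5% on vaccine (18.0/12.0 = 1.50; 18.5/14.2 = 1.30). In 25 patients that is 3.0–3.6 against 4.5–4.6.
- Half stop: 16.0–17.1% against 19.0–19.3% (1.19 to 1.13).

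**Step 5: first quarter.** The earliest end of observation is day 106, so both arms are fully observed to day 91.

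**Step 6: effect of an at-risk denominator, all stopping.** At day 274 the shares still observed are 60.0% and 90.0% (A), 68.2% and 92.4% (B), and 77.5% and 94.9% (C). The vaccine/placebo ratio becomes:
- A: 1.00
- B: (0.914/0.924)/(0.646/0.682) = 1.04
- C: (0.921/0.949)/(0.673/0.775) = 1.12

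In the second quarter (days 92 to 182), patients who stopped at day 85 are still observed at day 92, so the divisor does not change. The shares are 84.4–90.9% on placebo and 96.5–98.0% on vaccine, and a ratio of 1.14 (A) to 1.08 (C) remains. Patient-time within the period removes this remainder if the rate is constant.

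**Step 7: why not one patient-year rate over the whole year.** Stoppers at looks 1 to 4 have had 12, 15, 18 and 18 doses; completers have 21. Mean doses are 18.8 (placebo) and 20.5 (vaccine), over 297 and 364 mean days (A) or 313 and 369 (B). Doses per day are 0.0633 against 0.0562 (ratio 1.13) or 0.0599 against 0.0555 (1.08). If AEs follow doses, a pooled rate would be 8 to 13% higher on placebo with equal risk per dose.

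**The case against.** The strongest reply is that the size rests on a stopping share that the plan does not fix. Recurrence need not end dosing, and if no failing patient stops there is no bias. That stands, and it is why the result is given as a range. Progression, however, must end dosing, so a share of zero is unlikely.

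Second, AEs are still recorded at the Week 25, 37 and 49 visits, and the End of Treatment visit may be timed from early discontinuation rather than from the last dose. That favours rules B and C, which give the lower ratios.

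Third, crude incidence over the safety set is a valid answer to how many patients ever had a reported event. This stands for the overall table. There, a 30% AE would show as about 28% on vaccine and 24% on placebo, roughly one patient in 25. Exposure (SAP 8.1) and reasons for stopping (SAP 6.1) are also tabulated, so unequal dosing will be visible. A reader still could not correct the quarterly percentages from those tables.

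Fourth, the by-quarter table is specified only in the protocol; SAP 8.2 does not repeat it. But SAP section 8 names time period in its counting rule, so the rule would apply to that table.

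A reader might also infer that Arm 4 is the worst affected. The documents do not support this. They assume no DFS for Arm 4. The 39% and 62% in Protocol 1.1 are background recurrence-free rates by risk group. In the second model with all failing patients stopping, 38% failing gives a fourth-quarter figure of 12.4–14.5%, close to placebo, and 61% failing gives 7.8–11.1%. Arm 4 is also non-randomized, receives no BCG, and has a safety definition (Protocol 12.4.6) that names no comparator.

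**Conclusion.** The point holds for AE summaries by time period. Followed as written, the plan counts patients outside AE observation as event free in later quarters. With 60% against 90% DFS and equal true AE rates, the late-period percentage on vaccine would be about 1.4 to 1.5 times that on placebo if all failing patients stop. Under the most generous recording cut-off that falls to 1.3 to 1.4. With half stopping it is about 1.15 to 1.2 times, and with none there is no difference. The first quarter is essentially untouched.

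These figures assume a constant AE rate, equal across arms, and failures detected only at the scheduled cystoscopies. With 25 patients per arm the artefact amounts to one or two patients for a 20% event, so in any single term it could not be told apart from chance. The risk lies in a consistent late pattern across terms.

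The effect falls mainly on all-cause, serious and high-grade events. Related AEs are recorded without a time limit, although a patient off treatment cannot have a related AE from a dose not given. It would be wrong to conclude that the plan hides vaccine harm: in Arms 1 to 3, under the design assumption, the distortion counts against the vaccine. The size in Arm 4 is unknown.

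**What to change.** In SAP section 8, except by-period AE summaries from the full-group rule. For the by-quarter table, use as denominator the patients still under AE observation at the start of the quarter, and print that number for each arm and quarter. Define the end of all-cause AE observation once; for this the four weeks in the protocol and the 30 days in SAP 8.2 must be reconciled.

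Keep the crude full-group percentage for overall incidence. As an optional supplement for all-cause TEAEs, Grade 3 or higher TEAEs and SAEs, show incidence per patient-time within each quarter. This also deals with patients who leave during a quarter. Do not pool patient-time over the year, because 15 of the 21 doses fall by Week 16. Do not apply it to related AEs, whose observation has no defined end.

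The cost is a little programming and a denominator that varies across quarters. Dose dates and AE dates are already collected.

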8.1 Extent of Exposure

Treatment exposure will be summarized by treatment group, in the following ways:

- (1) Number of doses of vesigenurtacel in phase I and vesigenurtacel/placebo in each arm in phase II, overall and also separately for induction phase and for maintenance phase.
- (2) Cumulative doses of vesigenurtacel in phase I and vesigenurtacel/placebo in each arm in phase II, overall and also separately for induction phase and for maintenance phase.
- (3) Cumulative BCG dose in arms 1,2,3 in phase II, overall and also separately for induction phase and for maintenance phase.
- (4) Number of patients receiving the full dose vs partial dose of vesigenurtacel and BCG in induction and maintenance up to 12 months since the start of induction of BCG. The number of patients receiving additional maintenance (as per physician's choice) beyond 12 months from the start of induction of BCG will also be summarised.
- (5) Number of dose reductions / dose delays in vesigenurtacel and BCG

8.2 Adverse Events

TEAEs will be defined as events that occur on or after the first dose of study medication. The Medical Dictionary for Regulatory Activities (MedDRA) coding dictionary will be used for the coding of AEs (version 18.0 or higher). The severity of TEAEs will be graded on a scale of 1 to 5 according to the adult NCI Common Terminology Criteria for Adverse Events (CTCAE version 4.0) where higher grades indicate events of higher severity. Adverse events will be summarized by grade according to the worst grade experienced. TEAEs, serious or CTCAE grades -5 TEAEs, and TEAEs related to therapy will be summarized overall and by system organ class and preferred term by treatment group. A listing of AEs leading to treatment discontinuation including the patient number, site, treatment group, start date and study day of AE, severity, relationship to study regimen, action taken, and outcome of AE will be provided. Additional summary table summarizing preferred term may be provided if warranted.

For summary purposes, AEs will be defined as all reported events with a start date on or after Study Day 1. All AEs are collected through 30 days post last dose (treatment-emergent AEs). All AEs will have their relationship to study drug (BCG or HS-410) assessed by the investigator as related or not related. Adverse events will be categorized and summarized according to their highest relationship to study drug.

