Phase 2: Dosing in Phase 2 will begin when all 10 patients have been dosed in the Phase 1 cohort, at least 6 patients in that cohort have completed the Week 7 safety assessments, and the Data Monitoring Committee (DMC) has met to review this data and agreed it is safe to advance to Phase 2. A total of 100 patients will be assigned to four groups: 75 who will receive BCG will be randomized to arms combining either low dose vesigenurtacel-L, high dose vesigenurtacel-L, or placebo, respectively, with induction and maintenance BCG; 25 who will not receive BCG will be enrolled in the high dose vesigenurtacel-L monotherapy arm.

In the randomized arms, treatment will commence within 6 weeks of the most-recent TURBT or fulguration for patients with papillary disease and staging procedure for patients with CIS only. Patients will be treated during an induction phase with weekly intravesical BCG and intradermal blinded study product (vesigenurtacel-L or placebo) for 6 weeks followed by 6 weekly injections of blinded study product alone. During a subsequent maintenance phase, patients will receive an additional three courses of three once-weekly blinded study product injections in combination with intravesical BCG approximately 3, 6, and 12 months after initiating induction BCG. Patients may receive additional courses of maintenance BCG in long-term follow-up at the investigator's discretion but should not receive any other cancer therapy prior to disease recurrence/progression.

In the monotherapy arm, treatment will commence within 6 weeks of the most-recent TURBT or fulguration for patients with papillary disease and staging procedure for patients with CIS only. Patients will be treated during an induction phase with weekly intradermal vesigenurtacel-L for 12 weeks. During a subsequent maintenance phase, patients will receive an additional three courses of three once-weekly vesigenurtacel-L injections approximately 3, 6, and 12 months after initiating induction vesigenurtacel-L.

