#### **5.1.2 Phase 2**

In order to continually monitor safety during the Phase 2 portion, the DMC will review (unblinded) all available safety data after one patient has been randomized to each of the active arms and has completed four weeks of treatment and then after 3, 6, and 12 patients in each randomized treatment group have completed the Week 7 assessment. Subsequently the DMC will review all available safety data at regular three-monthly intervals until study completion or should they determine that review is no longer necessary. Additionally, the DMC will convene on an ad-hoc basis should any patient experience a Grade 3 or higher adverse event (considered by the investigator to be related to vesigenurtacel-L) at any time during the study. Depending on emerging data, the DMC will have the authority to suspend allocation to a particular study treatment and require that additional patients are studied in a particular arm or at a particular dose level of vesigenurtacel-L, in order to further characterize the safety profile.

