## 8.5 Treatment Assignment

The definitions of the randomized arms relative to the intended intervention to be used in those arms will be as follows:

Phase 1: Vesigenurtacel-L Low Dose:  $1 \times 10^6$  cells per dose

Phase 2:

- Arm 1: Vesigenurtacel-L consisting of  $1 \times 10^6$  cells per dose + BCG

- Arm 2: Vesigenurtacel-L consisting of  $1 \times 10^7$  cells per dose + BCG
- Arm 3: Placebo (containing intralipid for blinding, but no cells) + BCG
- Arm 4: Vesigenurtacel-L consisting of  $1 \times 10^7$  cells per dose

[figure not shown]
In Phase 2, patients who will receive BCG will be randomized centrally to Arm 1, 2, or 3 using a stratified block design according to risk of recurrence (strata: high vs. intermediate risk) and CIS (strata: yes vs. no). Patients who will not receive BCG will be enrolled in Arm 4.

Due to delays in the batch release of certain doses of vaccine, the randomization schedule may be temporarily revised from a 1:1:1 randomization to a 1:1 randomization, with one arm being briefly suspended. During the period of revised randomization, each patient will maintain at least a 50% chance of receiving vaccine versus placebo. Randomization strata will remain unchanged. Upon batch release of the vaccine the randomization will return to the original 1:1:1 ratio. In order to maintain the study blinding, temporary closure of certain arms will not be disclosed outside of the DMC except as needed for Informed Consent documents.

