#### **11.8.5 Reporting Adverse Events**

The investigator will record all directly observed AEs and all AEs spontaneously reported by the study patient on the *Adverse Event* ECRF. In addition, each study patient will be questioned about AEs.

Each AE should be described in detail on the *Adverse Event* ECRF and SAEs on a *Serious Adverse Event* form and include the following information: start and stop dates, CTCAE v. 4.03 grading, relationship to study medication, action taken, and outcome. AEs should be recorded from time of first dose up to four weeks following the last dose of study medication regardless of the causal relationship to the study medication. AEs considered related to study medication should be recorded at any time regardless of when they occurred.

The investigator will also assess the possible relationship between the AE and the study medication as well as any concomitant medications according to the following criteria:

- Related: AE and administration of study product are related in time, and a direct association can be demonstrated.
- Not related: AE is clearly explained by another cause not related to study product.

Event outcome will be recorded using the following categories:

- Recovered/resolved
- Not recovered/not resolved
- Recovered/resolved with sequelae
- Fatal
- Unknown

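### SAP 8.2 rates relatedness to BCG or HS-410 jointly, so its related-AE tables do not isolate vaccine-attributed events or match the protocol's study-product definition

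*SAP*

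**What the plan says.** SAP 8.2 asks for one two-level judgement on each event: "relationship to study drug (BCG or HS-410) assessed by the investigator as related or not related". It then sets the summary rule: "Adverse events will be categorized and summarized according to their highest relationship to study drug". The tables built on this rating are specified as follows: "TEAEs related to therapy will be summarized overall and by system organ class and preferred term by treatment group". No table by individual agent is listed, and the SAE listing in SAP 8.3 also carries only relationship to study drug.

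The protocol uses a narrower reference. Section 11.8.5 gives the causality category as "Related: AE and administration of study product are related in time, and a direct association can be demonstrated". Study product there means the blinded injection and is named apart from BCG, as in section 3.1: "weekly intravesical BCG and intradermal blinded study product (vesigenurtacel-L or placebo) for 6 weeks". The Grade 3 or higher events that trigger an ad hoc DMC meeting under section 5.1.2 are those "considered by the investigator to be related to vesigenurtacel-L".

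Two further provisions matter. The control is "Arm 3: Placebo (containing intralipid for blinding, but no cells) + BCG" (protocol 8.5), so all three randomized arms receive BCG. SAP section 8 also plans a table that ignores attribution: "A descriptive summary of all Treatment emergent adverse events (TEAEs) by system organ class and preferred term will be provided".

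**The concern.** A related-AE table is normally read as the investigators' view of what the investigational product caused. Under SAP 8.2, an event blamed only on BCG enters the same cell as an event blamed on the vaccine, in the placebo arm as well as the vaccine arms. The blinded product in Arm 3 is not named in the definition at all.

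Two things are at stake. First, the final related-AE tables would not count the same events as the protocol's causality definition, so the two could not be reconciled. Second, SAP section 8 counts each patient once per category. A patient who already has a BCG-attributed event gains nothing in the any-related row when a vaccine-attributed event follows, so part of the contrast between vaccine and placebo disappears from that row.

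**Working it through.** **Step 1: the definitions side by side.**

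| Place | Related to what |
|---|---|
| SAP 8.2 | BCG or HS-410, one rating, highest relationship summarized |
| Protocol 11.8.5 | Study product (vesigenurtacel-L or placebo) |
| Protocol 5.1.2, ad hoc DMC trigger | Vesigenurtacel-L |
| Protocol 12.4.1, planned AE tables | Therapy, not further defined |

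The first row cannot be reduced to the second or third without a separate rating for the injected product. SAP 8.1 already separates vesigenurtacel/placebo from BCG for exposure, but 8.2 does not do so for causality.

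**Step 2: how far merging dilutes the contrast.** The plan states no figure on this point, so there is nothing to reproduce. What follows is an illustration.

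Inputs from the documents:
- 25 patients per arm (protocol 3.3).
- BCG in Arms 1, 2 and 3 (protocol 8.5).
- Each patient counted once per category (SAP section 8).

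Assumed inputs:
- Events attributed to the injected product occur in v₁ = 30% of vaccine patients and v₀ = 5% of placebo patients.
- BCG-attributed events occur in a share b of patients, the same in every arm and independent of the injected-product events.

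The documents give none of these rates. Protocol 1.2 describes BCG side effects only in words.

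Merged rate in an arm = 1 − (1 − b)(1 − v).

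Difference = [1 − (1 − b)(1 − v₁)] − [1 − (1 − b)(1 − v₀)] = (1 − b)(v₁ − v₀) = (1 − b) × 25 points.

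Example at b = 70%: placebo 1 − 0.30 × 0.95 = 71.5%; vaccine 1 − 0.30 × 0.70 = 79.0%; difference 7.5 points, or 25 × 0.075 = 1.9 patients.

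| b | Placebo + BCG | Vaccine + BCG | Difference (points) | Patients of 25 | Exact Fisher power |
|---|---|---|---|---|---|
| 0 | 5.0% | 30.0% | 25.0 | 6.3 | 69% |
| 10% | 14.5% | 37.0% | 22.5 | 5.6 | 47% |
| 30% | 33.5% | 51.0% | 17.5 | 4.4 | 27% |
| 50% | 52.5% | 65.0% | 12.5 | 3.1 | 16% |
| 70% | 71.5% | 79.0% | 7.5 | 1.9 | 9% |
| 90% | 90.5% | 93.0% | 2.5 | 0.6 | 2% |

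The b = 0 row is also what a separate HS-410/placebo table would show under these assumptions. The last column is a one-sided test at 0.05, 25 vs 25, by enumeration of all tables. It is only a yardstick of visibility, because SAP 5.5 plans no safety tests.

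**Step 3: other assumed rates.** With 20% vs 0% instead of 30% vs 5%, the 20-point difference becomes 14, 6 or 2 points at b = 30%, 70% or 90%. The factor (1 − b) is the same.

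**Step 4: which rows are affected.** The factor applies row by row. In a preferred-term row to which BCG contributes nothing, b = 0 and nothing is lost. The dilution falls on the any-related row and on terms that both agents can produce.

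**The case against.** A reader might infer that the related-AE tables cannot show what the vaccine adds, or that BCG toxicity swamps it. The documents do not support either reading. BCG is common to Arms 1 to 3, so even a merged table compared with Arm 3 estimates the vaccine's addition, in diluted form. Swamping would need a high b, and no BCG event rate is given. The tables are also split by system organ class and preferred term, and injection site reactions are summarized separately by type and grade (SAP 8.5).

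The secondary safety objective does not rest on attribution: protocol 12.4.7 defines combination safety as AE/SAE proportions against placebo + BCG, with no relatedness filter.

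A reader might also infer that the DMC trigger or the stopping rule is compromised. Both act on individual reports during the trial, not on final SAP tables, and section 5.2.2 speaks of related SAEs without naming the agent. Nor does the wording make Arm 4 non-comparable: that arm is non-randomized and open-label by design.

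The protocol is not fully consistent either. Section 12.4.1 says only that events related to therapy will be tabulated, and 12.2 counts BCG as treatment when defining the safety population. Finally, the highest-relationship rule may mean that separate ratings are collected and collapsed only for the summary, or that the worst of repeated events is taken.

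All of this stands, and it limits the point to one set of tables. It does not remove the mismatch: as written, SAP 8.2 commits to no summary of events attributed to the injected product alone.

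**Conclusion.** The point holds as a defect in the definition and content of the related-AE tables. It is not a failure of the safety comparison as a whole. SAP 8.2 pools two agents in one category, omits placebo from the definition, and departs from the reference used in protocol 11.8.5 and 5.1.2.

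The loss is a factor of (1 − b) in the any-related row and in shared terms, and nil where BCG contributes no events. For an assumed 25-point contrast the remaining difference runs from 22.5 points at b = 10% to 2.5 points at b = 90%. These sizes rest on assumed rates, on the same b in each arm, on independence of the two kinds of event, and on investigators who are blinded to vaccine or placebo being able to tell the agents apart. If vaccine-attributed events cluster in patients who also have BCG-attributed events, the dilution is greater; if they fall mainly in other patients, it is smaller.

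The change is worth making because the all-causality table, although it is the right main comparison, carries the same BCG background and cannot stand in for a product-specific table.

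**What to change.** In SAP 8.2:

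1. Replace the joint reference to BCG or HS-410 by relationship to HS-410/placebo and, separately, relationship to BCG.
2. Confirm that the CRF records the two ratings separately. Protocol 11.8.5 already asks the investigator to judge study medication and concomitant medications.
3. Tabulate related TEAEs, related SAEs and related Grade 3 or higher TEAEs by (a) relationship to HS-410/placebo, stated to correspond to protocol 11.8.5, (b) relationship to BCG, and (c) either.
4. Say what highest relationship means: across agents, across repeated events in a patient, or both.
5. Keep the all-causality comparison with Arm 3 as the main safety comparison.

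The cost is a set of extra tables and, if per-agent ratings are not already collected, one added causality field. Design, treatment and sample size are unaffected.
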